Recently a small randomized trial in cardiac surgery patients found a significant reduction in postoperative delirium (31% to 3%) when sub-anaesthetic doses of ketamine (0.5mg/kg) were given upon induction [13]. The same group further published data for improved postoperative cognitive function with ketamine in cardiac patients [13]. A follow up randomized prospective study in cardiothoracic patients looking at ketamine and delirium is currently recruiting (PODCAST).

Ketamine's benefits are thought to be based on its NMDA antagonism, HCN1 inhibitory effects and its anti-inflammatory properties [14]. Multiple studies have shown decreased post-operative pain with decreased post-operative opioid use when ketamine was administered during the surgery [15]. Interestingly a recent study showed that a single dose of ketamine had a prolonged two week lasting effect on patients with refractory depression [16].

Ketamine is a drug that has been in use for more than half a century, is inexpensive and has a wide margin of safety.

We are proposing a prospective randomized placebo controlled study to elucidate the effects of ketamine on postoperative delirium in the head and neck cancer population receiving “flaps”, administered peri-operatively.

4. Objectives:

Primary Aim:

Optimize our intraoperative treatment protocol for head and neck cancer patients to reduce the incidence of delirium and associated postoperative cognitive dysfunction. The hypothesis is that ketamine decreases delirium postoperatively in this high risk surgical patient population.

Secondary Aims:

1. Determine the dose response relationship for intraoperative ketamine and delirium reduction. Our hypothesis is that higher dose ketamine will lead to a more profound reduction in postoperative delirium.
2. Determine if a single dose of ketamine will reduce post-operative pain and opioid requirements. Our hypothesis is that the higher dose of ketamine will lead to a more profound decrease in objective pain scores.
3. Determine if raw EEG data can predict postoperative delirium during general anesthesia. Our hypothesis is that EEG patterns will correlate with incidence of post-operative delirium.
4. Evaluate length of ICU and length of hospital stay (done by medical chart review). Our hypothesis is that ketamine administration will not increase ICU/hospital stay.

5. Innovation, Impact & Leverage.

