The successful completion of this study will provide critical data on a therapeutic and/or prophylactic effect of perioperatively administered ketamine on postoperative delirium. Delirium has been associated with increased length of ICU and hospital stay, increased cognitive impairment/decline and mortality. Despite increasing evidence of ketamine's ability to reduce postoperative delirium in cardiac patients, its opioid sparing effects and decreased postoperative opioid needs, ketamine is not widely used. Clinicians are concerned that psychoactive properties (e.g., hallucination and dissociative states)

interfere with post-operative cognitive function. These side effects however are rarely seen when ketamine is used in subanaesthetic doses.

Additionally, EEG data will be used to determine if this tool can be a possible predictor of delirium.

Currently, the most common way to monitor brain function during surgery is via processed electroencephalogram (EEG) monitors (SEDLine). These devices use frontal or fronto-temporal EEG electrodes, to measure the electrical activity of the brain. A special computer program translates these brain waves into a dimensionless number that roughly correlates to the dose of anesthesia administered. A purpose of our research is to utilize the electrical information from the raw EEG signals to determine if EEG patterns can predict a propensity to develop postoperative delirium. Our approach is to probe deeper into the analysis of the EEG signal than simply depth of consciousness by developing a taxonomy of specific states leading up to and through emergence.

EEG technology measures the electrical potential generated by synaptic input onto the dendrites of cortical neurons. Although higher frequencies are attenuated somewhat by the skull, a wide range of frequencies can be observed even with the abbreviated montage typical for the commonly available devices. With a minimal amount of effort the EEG file is available for download from the device via USB stick. The sensors are pre-packaged with gentle adhesive and applied to the patient's forehead while the patient is awake and removed with a minimal amount of discomfort (similar to a Band-Aid).

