This monitoring plan is appropriate, since ketamine, an anesthetic drug, has an excellent safety profile and is commonly used in anesthetic practice. In addition, the doses used in this study are unlikely to cause major or minor side effects (e.g., emergence reactions, hallucinations).

10. Statistical analysis

a. Sample size:

It was assumed about 30% delirium incidence in our population by standard care [1] [2] [3].

Estimating 5-8 oropharyngeal cancer surgeries per week with a conservative enrollment rate of 50%, we will be able to recruit 130-208 patients in 12 months. We plan to enroll about 85 eligible patients in order to achieve 20 completed patients in each randomized group. For this pilot study, with this sample size we will have 85% statistical power under significant level of 0.05 to detect delirium incidence rate drop at least 30% (placebo) to 5% (two treatment arms combined) by one-sized Mantel Haenszel test, and such effect size is supported by an existing trial [13].

b. Data analysis:

For primary aim, the incidence of delirium will be calculated in each of three randomized group with 95% confidence interval (CI), and compared between each ketamine treated group with placebo group through Fisher's exact test. For secondary aims, the dose response effect of ketamine on delirium reduction will be tested by Cochran-Armitage trend test. For other outcomes, such as pain (and/or change from baseline), MMSE (and/or change from baseline), EEG data, length of stay (LOS), and use of narcotics will be first described by summary statistics (mean, median, standard deviation, frequency, and etc.) by three randomized groups and then compared by Chi-square test/Fisher's exact test, ANOVA, or Krusal-Wallis test wherever appropriate. The analysis will be

conducted by the Biostatistics and Bioinformatics Shared Resource at Winship Cancer Institute.

The Winship OnCore system will be used for data entry and analysis.

11. Confidentiality

The privacy of the research subjects will be ensured through standard procedures for securing research data. Whenever possible, a study number, rather than a name, will be used on study records. Identifying information will not appear when we present or publish the study results. All interactions with subjects during the study will occur in a private setting. Only Emory owned computers will be utilized to store data with any identifiers and these are compliant with the Emory disc encryption policy.

12. Literature:

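### Aim 3 sets out to determine whether EEG predicts delirium with about 8 expected cases, no lead feature and no correction for selection, so an apparently useful predictor can readily arise by chance

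*Combined protocol and SAP*

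**What the plan says.** Secondary Aim 3 (section 4) is to "Determine if raw EEG data can predict postoperative delirium during general anesthesia", with the hypothesis that EEG patterns will correlate with delirium. Section 5 repeats the purpose, to "determine if EEG patterns can predict a propensity to develop postoperative delirium", and gives the approach as "developing a taxonomy of specific states leading up to and through emergence". It adds that the analysis is quantitative and uses several frontal electrodes. Section 6 lists, as secondary outcome 4, an off-line EEG analysis correlated with delirium.

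Section 10b mentions EEG once, in a list of outcomes to be summarised and compared across the three randomized groups. The documents contain no list or cap of EEG features, lead feature, time window, model, performance measure, multiplicity control or validation step for Aim 3.

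Section 10a plans for "20 completed patients in each randomized group", with delirium in 30% on placebo and 5% in the two ketamine arms combined.

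The Abstract (section 2) describes the off-line EEG analysis as being done in the patients who become delirious. Read literally, that leaves nobody to compare them with, and it does not fit sections 4 and 6.

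**The concern.** A comparison of EEG by treatment arm cannot say whether EEG predicts delirium. Adding an EEG-by-delirium comparison would close that gap but leave another. Several electrodes, a range of frequencies and a set of states still to be defined give many possible features, and the number of delirious patients is small. If features are chosen because they separate those few patients from the rest, and performance is reported in the same patients, the result is biased upward. The report could then present an EEG signature that a reader cannot tell from selection. Even without selection, so few events leave the estimate too imprecise to support the word used in the aim.

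**Working it through.** **1. The plan's own figure.** Inputs from section 10a: 20 placebo and 40 ketamine completers, rates 30% and 5%, "under significant level of 0.05", "by one-sized Mantel Haenszel test" (read as one-sided). Let a and b be the delirium counts on placebo and ketamine, and m = a + b. The test statistic is Z = (a − 20m/60)/√v, with v = 20·40·m(60 − m)/(60²·59). Summing the binomial probabilities of all outcomes with Z > 1.645 gives 84.8%, against the stated 85%. The inputs are therefore read as the plan intended.

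**2. Expected events.**
- Planned effect: 20 × 0.30 + 40 × 0.05 = 6 + 2 = 8 of 60 (exact central 90% range 4 to 12).
- No ketamine effect, 30% in every arm: 60 × 0.30 = 18.

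**3. Chance of at least one p<0.05 when no feature carries information.** For k independent features this is 1 − 0.95^k: 5% for k = 1, 23% for 5, 40% for 10, 51% for 14 and 64% for 20. The number of features k and their correlation are assumptions. Simulated rank tests with 8 events in 60 patients give about:

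| Null features | Independent | Correlation 0.5 | Correlation 0.8 |
|---|---|---|---|
| 10 | 39% | 28% | 18% |
| 20 | 61% | 43% | 24% |
| 50 | 91% | 63% | 32% |

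More events do not cure this, because it comes from the number of tests. With 18 events and 20 independent features the chance is still about 64%. One feature fixed in advance keeps it at 5%.

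**4. Size of the chance AUC.** In the same simulations with 8 events, the mean best AUC among independent null features is 0.71, 0.73 and 0.77 for 10, 20 and 50 features. At correlation 0.8 it is 0.66 to 0.69. The event count matters here: the best of 20 independent null features reaches AUC 0.70 in about 75% of simulated trials with 8 events, but in 24% with 18.

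**5. Precision of one pre-named feature (Hanley-McNeil).** With m events and n non-events, SE² = [A(1 − A) + (m − 1)(Q₁ − A²) + (n − 1)(Q₂ − A²)]/(mn), where Q₁ = A/(2 − A) and Q₂ = 2A²/(1 + A). At A = 0.70, Q₁ = 0.538 and Q₂ = 0.576.
- m = 8, n = 52: SE = 0.109, half-width 1.96 × 0.109 = 0.21, interval 0.49 to 0.91.
- m = 18, n = 42: SE = 0.078, half-width 0.15, interval 0.55 to 0.85.

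**6. Treatment arm.** Under the planned effect 6 of the 8 events are on placebo. Any EEG feature that differs by arm would then track delirium through treatment, even with no link within arms. Comparing only within placebo and within pooled ketamine leaves 6 × 14 + 2 × 38 = 160 of the 8 × 52 = 416 event/non-event pairs, so an arm-stratified interval can be expected to be wider than the one in step 5.

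**The case against.** The strongest reply is that the documents do not describe a search. The taxonomy could be built without looking at delirium status. In that case building it adds no optimism, and only the number of states later tested matters. Section 6 speaks of correlation, and no AUC or fitted score is planned. The study is a pilot, section 5 calls EEG a possible predictor, and it says the value of EEG frequency analysis for this purpose is unknown. Features from neighbouring frontal electrodes are plausibly correlated, and 8 events is the count only if the large planned effect is real.

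Much of this stands. A reader might infer that a false predictor is bound to appear. The documents do not support that: neither the number of features nor their correlation is given, and the computed chance runs from 5% for one feature to about 91% for 50 independent ones. A reader might also infer that a multivariable model will be fitted and reported uncorrected. The documents do not say so; they say nothing either way.

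What does not stand is that the exploratory tone settles the matter. Aim 3 is worded as a determination, section 10 does not label the EEG work exploratory, and no rule prevents a broad search. At correlation 0.8, 20 null features still give about 24%, nearly five times the nominal 5%.

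**Conclusion.** The point holds as a risk that the plan leaves open, not as a certainty. Section 10b has no analysis that answers Aim 3, and nothing limits or corrects selection if one is added. With 8 events, a search over 10 to 50 null features gives an 18% to 91% chance of at least one nominally significant feature across the correlations considered, with a mean best AUC of 0.66 to 0.77. For independent features the chance passes one half at 14.

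The 8 events rest on the 30% and 5% rates in section 10a. With no ketamine effect there would be 18, which shrinks the chance AUC and narrows the half-width from about 0.21 to 0.15, but leaves the multiplicity problem. In neither case can about 60 patients settle whether EEG predicts delirium. The consequence is confined to a secondary aim; the primary delirium comparison is not affected.

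**What to change.** In section 10b, before EEG is linked to the delirium data:

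1. Name one EEG feature and one time window as the main predictor for Aim 3.
2. Analyse it by delirium status in all patients with usable EEG, delirious or not, and reconcile the Abstract with sections 4 and 6 on this.
3. Account for treatment arm, for example by stratifying placebo against pooled ketamine, and report the AUC with a 95% CI.
4. Label every other EEG state or feature exploratory and report how many were examined. Do any selection or fitting inside bootstrap or cross-validation, with the optimism-corrected AUC beside the apparent one.
5. State Aim 3 as a hypothesis-generating estimate of the association between EEG and delirium.

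The cost is protocol and SAP wording and modest extra analysis, with no new patients or measurements. The downside is that reported EEG performance will look less favourable, and the arm-stratified interval will probably be wide.

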Up to 100 patients will be consented in order to achieve at least 60 patients who will be randomly assigned and administered 0.5 mg/kg, 1mg/kg or placebo intravenous bolus after induction of anesthesia. A processed EEG device (SEDline, Masimo Corporation) will be used to gather raw EEG data for off line analysis among patients developing post-operative delirium. Patients will be screened for delirium with the CAM-ICU once per shift (3 times daily) for three days postoperatively. Currently, the CAM- ICU is performed by ICU nursing and documented in the electronic medical chart. Both CAM-ICU screens and SEDLine monitoring are part of the usual and customary practice associated with these cases at EUHM and it would be unusual for a case such as this to be performed without this clinical data. Pain will be assessed according to hospital protocol and postoperative opioid consumption will be determined from the medical charts.

Preoperative and postoperative cognitive assessment will be completed at the ENT clinic preoperative, and postoperative follow up visit (done by research assistant). Adverse

effects (e.g., hallucinations or nightmares) will also be evaluated for three days postoperatively.

Chart review, data collection/entry will be done by [name], research assistant and the research staff.

3. Background and Significance:

Delirium is a frequent post-operative complication of major surgery with a reported incidence of 10-70 % [1] [2] [3]. After major head and neck cancer surgeries the incidence of delirium is reported to be over 25% [3]. Delirium is associated with increased morbidity and mortality, prolonged length of hospital and intensive care unit (ICU) stay and functional and cognitive decline [4] [5] [6] [7]. A history of dementia or depression, chronic medical illness, male gender and age>60 years are consistently described as risk factors for delirium [8] [9]; in the head and neck cancer patient population length of surgery and alcohol consumption have been identified as well [3] [10]. Currently there is no effective prophylactic treatment for delirium identified. Even the treatment of delirium remains difficult [11]. A Cochrane review on delirium prevention in hospitalized patients came to the conclusion that there is a paucity of research in this area resulting from difficulties in delirium detection and confounding factors like pre-existing cognitive impairment or multiple medical problems [12].

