1. Pre- and postoperative cognitive dysfunction (assessed in ENT clinic at pre- and post-operative visits or at anesthesia preoperative clinic) with the Mini-Cog, Mini-Mental Status Examination (MMSE) and the Cognitive Failure Questionnaire (CFQ).
2. Pain assessment (Prior to surgery (baseline assessment upon study enrollment in ENT clinic) and postoperative days 0-3 (afternoon/evening on postoperative day 0, and POD 1-3 per Emory protocol every 4 hours). Assessed by observer-based Behavioral Pain Scale or Behavioral Pain Scale (Non-Intubated) with subsequent administration of patient-reported Visual Analog Scale.

October 8, 2019

3. Post-operative use of narcotics (assessed POD 0-3 from medical chart)
4. Off line EEG analysis to correlate with postoperative delirium

7. Participant Selection

Inclusion criteria:

Inclusion criteria:

1. Patients 18 years of age and older, with otolaryngeal cancer receiving surgery with general anesthesia.

(Please note we are purposefully including patients with higher predisposition to delirium as we are investigating potential preventive strategies for this diagnosis of multiple etiologies. Patients at higher risk of delirium (e.g., advanced age, chronic hypertension) will be included in our study. Additionally, other common risk factors that exist in this patient population (e.g., alcohol or nicotine use) are thought to contribute to delirium postoperatively. [19])

2. Competent to provide informed consent.

Exclusion criteria:

1. Emergency surgery
2. Monitored Anesthesia Care (i.e., regional anesthesia alone without plans for general anesthesia)
3. Surgery involving the eye, eyebrow, forehead, or frontal scalp near the sensor placement
4. Poor health literacy (see next section)
5. Patients with an allergy, or have experienced any drug reaction to ketamine will be excluded.
6. Pregnant or lactating patients
7. Patients in active alcohol withdrawal
8. Patients with chronic pain who are taking buprenorphine

Subject Replacement

Subjects who are not admitted to the Intensive Care Unit after surgery, will be replaced, but will be followed per protocol through the final visit 2-6 weeks post-operatively.

Recruitment Plan/Eligibility Screening:

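### Patients with no planned ICU stay can be randomised and dosed, although the primary outcome is recorded after the recovery room only in the ICU and those not admitted are replaced

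*Combined protocol and SAP*

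**What the plan says.** **Who may enter.** Section 7, inclusion criterion 1: "Patients 18 years of age and older, with otolaryngeal cancer receiving surgery with general anesthesia". Neither the inclusion nor the exclusion list mentions extent of surgery, flap reconstruction or a planned ICU stay.

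**Where the outcome is recorded.** Section 6 defines the primary outcome as delirium by CAM-ICU on postoperative days 0-3. Section 8 gives two recovery-room screens, then screening during the ICU stay, with chart data collected for days 1-3. Appendix A, footnote 4, limits the scheduled scores for days 0-3 to those available from the ICU stay.

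**What happens to non-ICU patients.** Section 7, Subject Replacement: a patient who does not go to the ICU is replaced but stays in follow-up to the clinic visit. Randomisation is on the morning of surgery, before the operating room (section 8), and study drug is given just after induction (Appendix A, footnote 1). Both precede any knowledge of actual ICU admission.

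**What the sample size assumes.** Section 10a: "It was assumed about 30% delirium incidence in our population by standard care". The target is "to detect delirium incidence rate drop at least 30% (placebo) to 5% (two treatment arms combined"), with 20 completed patients per group. The only head and neck figure is in section 3: "After major head and neck cancer surgeries the incidence of delirium is reported to be over 25"%. Section 3 also describes the study population, once, as the "head and neck cancer population receiving “flaps”, administered peri-operatively".

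**What is analysed.** Section 10b compares each dose with placebo. It does not say whether replaced patients are included.

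**The concern.** Eligibility, outcome measurement and replacement do not fit together. The protocol lets in patients whose primary outcome it has no means of recording beyond the recovery room, and finds out which ones they are only after treatment. It then leaves open how they are analysed, and each choice has a problem.

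- **Included:** there are no scheduled CAM-ICU data after the recovery room. If no record is read as no delirium, the observed incidence falls for a reason unrelated to ketamine.
- **Excluded:** the comparison is conditioned on ICU admission, which happens after dosing and could in principle be influenced by the study drug. The comparison is then no longer protected by randomisation.

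A second question concerns the planning rate. The incidences cited in section 3 are for major surgery, while criterion 1 is not limited to major surgery. If 30% is too high for the patients counted, the stated power is too high as well.

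**Working it through.** **1. Reproduce the stated power.** Inputs from section 10a: placebo 30%, combined ketamine 5%, 20 completed per group (so 20 versus 40), alpha 0.05, Mantel-Haenszel test, read as one-sided.

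For *a* events of 20 on placebo and *b* of 40 on ketamine, with m = a + b and N = 60:

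z = (a − 20m/60) / √[20 × 40 × m(60 − m) / (60² × 59)]; reject if z > 1.645.

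Power is the sum of Bin(a; 20, p₀) × Bin(b; 40, p₁) over all rejecting pairs. At p₀ = 0.30 and p₁ = 0.05 it is 84.8%, which agrees with the stated 85%.

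**2. Vary the placebo rate.** The documents give no delirium rate for lesser surgery and no case mix, so the lower rates are assumptions. The risk ratio is held at 5/30 = 1/6.

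| Placebo rate | Ketamine rate | Power, 20 vs 40 |
|---|---|---|
| 30% (plan) | 5.0% | 84.8% |
| 25% | 4.2% | 78.9% |
| 20% | 3.3% | 70.9% |
| 15% | 2.5% | 59.8% |

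One mixture for scale: if a quarter of counted patients had a 10% rate and the rest 30%, the placebo rate would be 0.75 × 30% + 0.25 × 10% = 25%.

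**3. When the table applies.** It applies if the 20 counted patients per group have a lower rate, for example because some ICU patients had less extensive surgery. It does not describe replaced patients analysed in addition to the 20. Suppose 5 such patients per group were added with no delirium recorded (assumed). The placebo rate would be (20 × 0.30 + 0) / 25 = 24%. The formula in step 1, with 25 versus 50 patients and 24% versus 4%, gives 84.1%. Power barely moves, because the expected events stay at six on placebo. What suffers is the incidence estimate, and the outcome is unobserved for those patients.

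**4. Follow one patient through the protocol.** A patient having a short operation with no ICU plan meets criterion 1, is randomised, is dosed after induction, is screened in the recovery room and goes to a ward. No CAM-ICU is scheduled from then on. The patient is replaced but still followed. Section 10b does not say whether this patient is in the denominator.

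**5. Accrual.** Section 10a: 5 × 52 × 0.5 = 130 to 8 × 52 × 0.5 = 208 patients in 12 months, against about 85 to be enrolled. The share with planned ICU admission is not given. Reaching 85 within 12 months needs 85/208 = 41% to 85/130 = 65% of that pool. If half qualified (assumed), 65 to 104 would be available.

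**The case against.** **The replacement rule limits dilution.** This is the strongest point. Short operations without an ICU stay are what the rule addresses, and the target is 20 completed patients per group, so such patients appear not to count towards it. A reader might infer from criterion 1 that lower-risk patients will dilute the 30% rate and that 85% is wrong. The documents do not support that. The 85% is right for its inputs, 30% is stated as an assumption for this population, and no case mix or lower rate is given. At 25%, the edge of the cited head and neck figure, the loss is about 6 points. The rule does not settle the analysis set, and it acts after randomisation and dosing.

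**A reader might also infer that this is a flap trial with the wrong eligibility.** Flaps appear once, in a background sentence. The title, abstract, primary aim and approach speak of otolaryngeal or head and neck cancer patients without that limit. The hypothesis does refer to a high-risk group ("The hypothesis is that ketamine decreases delirium postoperatively in this high risk surgical patient population"), but correcting the background sentence would resolve the mismatch as well as narrowing eligibility would.

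**Nor are non-ICU patients wasted.** They have recovery-room CAM-ICU, intraoperative EEG, and cognition and pain assessments at the clinic visit, all of which serve the other aims.

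**Pilot status** makes broad eligibility a legitimate preference. It does not remove the need to say who is in the primary comparison.

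**Conclusion.** The point holds as a gap between eligibility, outcome measurement and replacement. Patients with no ICU plan can be randomised and dosed, are not scheduled for the primary outcome after the recovery room, and are replaced on a post-randomisation event with no stated place in the analysis. This follows from the text and needs no assumption.

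The effect on power is a sensitivity, not a demonstrated loss: 84.8% at 30%, about 79% at 25% and about 71% at 20%. The last two rest on assumed placebo rates, an unchanged risk ratio of 1/6, and 20 versus 40 counted patients. Certain dilution, or a breach of a flap-only design, would go beyond what the documents show. This is a low-cost improvement worth making; it does not invalidate the design.

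**What to change.** 1. Add to inclusion criterion 1: *planned postoperative ICU admission at the time of randomisation*. This selects on a fact known before treatment.
2. Define the analysis set in section 10. Keep in the primary comparison any randomised patient who unexpectedly does not reach the ICU, whether or not another patient is added, and state how CAM-ICU data missing outside the ICU will be handled. The same handling should cover patients who leave the ICU before day 3, whom criterion 1 cannot screen out.
3. Reconcile the flaps sentence in section 3 with section 7. A flap requirement is optional and a trade-off: if half the pool qualified (assumed), the low-end forecast of 65 would fall short of the 85 planned.
4. In section 10a, justify 30% for the patients who will be enrolled, and show power over a range of placebo rates.

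**Cost.** An eligibility amendment and some added text in section 10. The pool shrinks by an unknown amount, and fewer non-ICU patients contribute to the EEG, pain and cognition outcomes. Few patients who count towards the 20 per group are lost, because non-ICU patients are already replaced, and fewer replacements would be needed.
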